BMI	Body Mass Index
CEN	Complete Enteral Nutrition
CONSORT	Consolidated Standards for Reporting Clinical Trials
DHM	Donor Human Milk
ERDF	European Regional Development Fund
FFQ	Food Frequency Questionnaire
FT-OMM	Full term infants receiving OMM
HM	Human Milk
HULAFE	University and Polytechnic Hospital La Fe
IPAQ	International Physical Activity Questionnaire
KIDMED	Mediterranean Diet Quality Index
MedDietScore	Mediterranean Diet Score
OMM	Own Mother's Milk
PT-DHM	Pre-term infants fed with pasteurized DHM
PT-OMM	Pre-term infants fed with OMM
RBW	Recover of birth weight
T2DM	Type 2 Diabetes Mellitus
WP	Work Package
YAP	Youth Activity Profile

H2020 Contract No 818110

1. Preamble

The NUTRISHIELD platform will be validated through three clinical studies, where the efficacy of the NUTRISHIELD technology and methodology will be tested and validated. Three clinical studies, namely Study I, Study II and Study III, will be implemented in parts (Study III), or totally (Studies I and II) within NUTRISHIELD, each one aiming to produce input regarding different aspects of the NUTRISHIELD project. To this direction, different health conditions, population and settings will be used.

- Study I Obesity/Diabetes, will validate the nutrition algorithm developed based on personalised data of children having obesity and/or diabetes, through an observational and an intervention protocol.
- Study II Human milk, the results obtained from this observational study will be used to feed and then train the NUTRISHIELD personalized algorithm with data obtained from clinical settings, including both pre- and full-term infants, to be used as an asset for future reference.
- Study III- Cognitive decline, important associations of nutritional (abdominal fat measures) and other health-related parameters (epigenetics, inflammatory markers) will be revealed.

1.1. Objective of the deliverable

Deliverable D2.7 provides the report on the clinical trial protocols, developed to study the efficacy of NUTRISHIELD technology. The rationale of each study, the study design, involving a description of the study phases, sample characteristics, measurements and outcomes, where applicable, as well as the statistical analysis, and finally the expectations and role of each study within the context of the NUTRISHIELD project are recorded. The CONSORT 2010 (Consolidated Standards for Reporting Clinical Trials) checklist of information is used when reporting the protocols, as described in www.consort-statement.org. The study protocols serve as a model for the methodology to be ideally followed by the medical centers responsible for each study.

1.2. Content of the deliverable

The Deliverable D2.7 includes:

- Protocol proposed for Study I Obesity/Diabetes
- Protocol proposed for Study II Human milk
- Protocol proposed for Study III- Cognitive decline

Project Acronym: Nutrishield

Grant Agreement number: 818110 (H2020-SFS-2018-IA)

Project Full Title: Fact-based personalised nutrition for the young

2. Study I protocol: Personalised nutrition against obesity/diabetes for children

2.1. Background

Childhood obesity rates appear to have reached a plateau in western societies [1], yet the estimates remain alarmingly high. In the year 2016, some 124 million school-aged children worldwide were reported to be obese [1], a number possibly underestimated [2]. Excess body weight in childhood is associated with adverse health outcomes across the life span [3]. In light of the severe long-term effects of pediatric obesity [4], the disease calls for timely detection and therapy.

Having obesity is associated with metabolic abnormalities that predispose children to increased cardiometabolic risk [5]. This risk remains persistent during adulthood and is associated with an increased mortality risk [3]. Furthermore, obesity appears to consolidate during childhood and adolescence. Consequently, the obese child is highly likely to remain obese in adulthood [6].

Medical research has fairly recently suggested that children with obesity suffer from non-communicable diseases reportedly uncommon in childhood, that is type 2 Diabetes Mellitus (T2DM) [7, 8]. Other risk factors for the development of pediatric T2DM include familial history of the disease, being born to a mother with gestational diabetes and various metabolic abnormalities [9]. Unlike type 1 diabetes, T2DM is diagnosed at later stages and is associated with poor metabolic control [10], findings that could explain why youth with T2DM are in greater risk for developing earlier and more severe cardiovascular complications than children with type 1 diabetes [9].

Having diabetes, with or without concurrent obesity, calls for integrative lifestyle modification measures, with dietary management as cornerstone. Available guidelines for both youth obesity and diabetes agree on (i) the adherence to a healthful and culturally appropriate dietary pattern, (ii) the adoption of an active lifestyle, (iii) the promotion of adequate growth, and, when appropriate, (iv) weight reduction (up to 10% of initial weight) [11-13]. These modalities have been proven effective in the short term; lifestyle interventions in obese children have resulted in moderate weight reduction and ameliorated glycemic and cardiovascular indices [14-17]. Similar results have been produced for children

This document is part of a project that has received funding from the European Union's Horizon 2020 research and innovation programme under grant agreement No 818110. It is the property of the NUTRISHIELD consortium and shall not be distributed or reproduced without the formal approval of the NUTRISHIELD Management Committee. The content of this report reflects only the authors' view. EC is not responsible for any use that may be made of the information it contains.

with diabetes [11, 18-20]. However, the effects of a personalized lifestyle intervention based on measured biomarkers in urine or feces of these patients, or how these measures correlate to obesity and/ or diabetes biomarkers remain to be explored.

2.2. Objectives

The objectives of the Study I are:

- a) to assess the effectiveness of an intensive personalized dietary intervention in children with obesity and/or diabetes, versus a non-personalized one, in terms of health indices improvement, namely anthropometry, biochemical markers and dietary intake
- b) to identify possible links between biomarkers measured in urine or feces with obesity/diabetes markers

2.3. Methods

Overall study design, participants, Study Phase I and Study Phase II, sampling and statistical analysis are described in the following sections.

2.3.1. Study design

The details of the study design where optimized following discussions with the NUTRISHIELD partners (during the meeting held on Athens 9-10/4/2019, mails exchange and teleconferences) to better serve the project purposes. Small deviations from the Description of Action were decided regarding the study design related to the groups and the timeline without altering the overall goals of the study.

The proposed study is a two-arm, parallel, randomized controlled study, with a dietary intervention for children (8-18 year old) with obesity or diabetes (type I or II). It will be carried out in Ospedale San Raffaele hospital between M19 to M41. The study protocol will be approved by the Ethics Committee, and written informed consent will be obtained from all caregivers and/or participants. All procedures regarding volunteers' recruitment and participation, data security and handling will be in absolute accordance with the principles set under Work Package (WP) 9, concerning Ethical Requirements, and more specifically stated on Tasks 7.1 and 7.2 and D 7.2.

H2020 Contract No 818110

The study will be divided into two phases:

- 1. **Phase I**: the **Observational** phase, lasting at least four months. During this period children will be recruited and their diet and biomarkers will be assessed once, as described below. At the end of the observational phase and recruitment period, the study will pause for nine months (from M23 to M31) in order to perform machine learning analyses, feed the platform and train the personalized nutritional algorithm with the results from the preceding assessments of the observational phase.
- 2. **Phase II**: the **Intervention** phase, lasting six months. During this period children recruited in the study will be randomly allocated to one of the two groups:
 - Group A (Intervention) will receive a NUTRISHIELD-derived personalized diet
 - **Group B (Control)** will follow the standard European dietary guidelines for obesity/diabetes, i.e. the usual care/control diet.

Diet as well as biomarkers and clinical data will be evaluated at the beginning and at the end of the intervention phase.

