2.3.3. Study Phase I

Phase I is the observational phase of the study, during which a thorough assessment of each participant will be performed.

H2020 Contract No 818110

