2.3.4. Study Phase II

2.3.4.1. Description of the Intervention

Personalized diet (Group A)

This intervention includes a personalized dietary plan derived from NUTRISHIELD platform. This plan will be based on the personalized nutrition algorithm taking into account genome analysis, dietary assessment, biochemical markers, socioeconomic status as well as any input having possibly emerged from the machine learning analyses from the evaluations performed during Study Phase I. In specific, in the beginning of the intervention period, taking into account the results from the evaluations performed in the observational period, a 4-week personalized dietary plan, derived as described above will be given to the children. Then, every month, for the following six months, visits will be arranged in the hospital with a window of ± one week, in order to perform the evaluations described below and the children to receive the new 4-week algorithm-derived dietary plans based on the previous month's evaluation. The intervention will be based on dietary guidelines presented in Table 1 [30], modified accordingly to address personal dietary, genetic and other needs, if important input emerges from Phase I.

Usual care diet (Group B)

The control dietary plan will be based on the same principles as the intervention diet [30], but without the use of the NUTRISHIELD platform and the personalized algorithm. Standard information and advice will be given instead by trained dieticians in face to face meetings. This phase will last six months and visits will be arranged once per month.

Table 2.1: Evidence-based guidelines on which intervention and usual care dietary plans will be based upon[30]

Guidelin	es
0	caloric restriction of 10% below energy needs
0	fat intake of 25-35% of total energy intake
0	saturated fatty acids <10% total energy intake
0	monounsaturated fatty acids >10% total energy intake
0	adequate mixture of n-6 and n-3 polyunsaturated fatty acids (PUFA, approximately 10 $\%$ of total energy
	intake)
0	fruit intake:
	o 1.5 cups per day for children 8-13 years old
	o 1.5 cups per day for girls aged 14-18 years
	o 2 cups for boys aged 14-18 years old
0	vegetables intake:
	o 1 cup per day for girls aged 8 years old
	o 1.5 cups per day for boys aged 8 years old
	o 2 cups per day for girls aged 9-13 years old
	o 2.5 cups for boys aged 9-13 years old
	o 2.5 cups per day for girls aged 14-18 years old
	o 3 cups per day for boys aged 14-18 years old

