2.3.4.2. Measurements

All children will be thoroughly evaluated at baseline (before the intervention begins) and post-intervention (after the end of intervention). Evaluation includes sociodemographic profile (baseline only), dietary and lifestyle habits, anthropometric measurements, microbiome, metabolome and genotype (baseline only) profiling. Sociodemographic assessment and genotype profiling will be performed only in the observational phase and will not be repeated during the intervention Phase I.

o Sociodemographic information

Sociodemographic information will be collected from all children at baseline [21, 22], as described above.

Dietary assessment

At baseline and post-intervention the most valid method as evaluated in study phase I will be used, as described above (2.3.3 Study Phase I, Measurements: Dietary assessment). Two methods of dietary assessment will be compared during Phase I, namely a 4-day food record (supported by a mobile app for food pictures uploading) and an extensive semi quantitative food frequency questionnaire (FFQ), primarily aiming at evaluating the validity of the FFQ against the 4-day food record.

[figure not shown]
Moreover, for the evaluation of adherence to the Mediterranean Diet, the KIDMED score will be used [24], as described above.

o Other lifestyle behaviors assessment

Physical activity level, sleep duration and smoking habits will be assessed as described above. Furthermore, children will report whether they have a TV set in their room, the intake of dietary supplements and whether they are medically diagnosed with dietary allergies or other diseases as described in the former section.

Anthropometric assessment

Children's weight will be measured on leveled platform scale to the nearest 0.5 kg and height on a wall-mounted stadiometer to the nearest 0.5 cm. BMI (kg/m²) will be calculated by dividing the weight in kilograms by the height in meters squared.

Medical history assessment

Children's medical history will be recorded by asking all the chronic conditions that they may have.

Genotype characterisation

A buccal swap sample will be collected from all children at baseline. In specific, standard buccal swab kits will be used to gather DNA sample for sequencing, as described in Deliverable 3.1.

Metabolome characterisation

For the characterisation of the children's metabolic profile, urine and blood samples will be collected as described in Deliverables 2.2 and 3.1.

Microbiome assessment

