2.3.6. Statistical analysis

Descriptive statistics will be used to present the characteristics of the participating children. Linear regression analyses will be performed with weight and BMI, as well as blood glucose, insulin, A1C, HOMA-IR as dependent variables and physical activity levels, children's and mother's smoking habits, nutritional status including energy intake, consumption of specific food groups and KIDMED score, medical history, genotype and metabolome as the independent variables.

Between Group comparisons for the baseline measurements of the phase II of Study I, will be performed using t-test or Mann-Whitney test, to ensure comparability of the Groups. Then, children

enrolled in the intervention diet will (Group A) be compared to those of the control diet (Group B), regarding their weight and BMI status as well as regarding the glycemic control as indicated by blood glucose, insulin, A1C, HOMA-IR (i.e., primary end points), using Repeated Measures Analysis of Variance (RMANOVA). Moreover, the 2Groups will be compared regarding various cardiometabolic risk factors such as total cholesterol, LDL cholesterol, HDL cholesterol, LDL/HDL cholesterol ratio and triglycerides, improvement in nutritional status including energy intake and consumption of specific food groups, as well as urine biomarkers, biomarkers of intestinal inflammation and microbiome profile, using the aforementioned method. All necessary adjustments (based on the baseline analyses) will be performed to ensure the robustness of the results.

The analyses will be performed by using STATA v15 software (STATA Corp LLL, College Station, TX, USA).

Finally, additional statistical analysis with the view of deriving additional insights and influences in personalised nutrition will be presented in D2.5.

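### Optional gain in precision: Phase I values exist for every randomised child, but the Study I analysis section states no use of them in the Group A versus Group B comparison

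*Protocol*

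**What the plan says.** Protocol 2.3.1 splits Study I into two phases. Phase I is the recruitment period (M19 to M22), in which "children will be recruited and their diet and biomarkers will be assessed once, as described below". Section 2.3.3 describes it as the phase "during which a thorough assessment of each participant will be performed". After a nine-month pause (M23 to M31), Phase II starts: "During this period children recruited in the study will be randomly allocated to one of the two groups".

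Phase II relies on each child having been through Phase I. Section 2.3.4.2 states: "Sociodemographic assessment and genotype profiling will be performed only in the observational phase". Section 2.3.4.1 says that Group A's first plan is prepared "taking into account the results from the evaluations performed in the observational period, a 4-week personalized dietary plan" being the result. No section provides for direct entry into Phase II.

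Phase II has its own two measurement waves: "Diet as well as biomarkers and clinical data will be evaluated at the beginning and at the end of the intervention phase" (2.3.1).

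Section 2.3.6 begins the trial analysis with "Between Group comparisons for the baseline measurements of the phase II of Study I", made by t-test or Mann-Whitney test. It then compares the groups on weight, BMI, glucose, insulin, A1C and HOMA-IR by repeated measures analysis of variance, with any adjustments that the baseline analyses suggest. It lists neither the time points in that model nor the covariates. The uses that the Protocol gives for Phase I results are training the algorithm (2.3.1), choosing the dietary method (2.3.3.1) and building the Group A plan (2.3.4.1).

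**The concern.** Blood values and short diet records vary within a child from day to day, so one baseline is a noisy measure of the child's usual level. A second value taken before randomisation can remove some of that noise from the group comparison. It cannot bias the comparison, because allocation is independent of it. The Phase I value is such a measurement and will be collected anyway.

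On a natural reading, the baseline in 2.3.6 is the Phase II baseline, so the Phase I wave plays no stated part in the randomised comparison. What is at stake is precision only: a somewhat narrower confidence interval for the group difference, with no extra measurement.

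**Working it through.** **1. The plan's own figure.** Inputs from 2.3.5.1: difference 15, SD 20 (0.75 SD), 40 per group, two-sided 5%.

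Power = Φ(0.75 × √(40/2) − 1.96) = Φ(3.354 − 1.96) = 0.918. With the noncentral t on 78 degrees of freedom it is 0.912. The stated power of at least 90% therefore reproduces, with no credit for any baseline. On the t calculation, 39 per group gives 0.905 and 38 gives 0.897.

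**2. Age of the Phase I value.** Phase I runs M19 to M22, and Phase II starts in M32. The gap is 9 months for a child assessed at the end of M22 and up to 9 + 4 = 13 months for one assessed at the start of M19. The Phase II baseline to end interval is 6 months.

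**3. Formulas.** Let r_BE be the correlation of Phase II baseline with end value, r_PE of Phase I with end value, and r_PB of Phase I with Phase II baseline. Residual variance, as a fraction of the end-value variance:

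- one baseline: 1 − r_BE²
- two baselines: 1 − (r_BE² + r_PE² − 2 r_BE r_PE r_PB)/(1 − r_PB²)

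The documents give none of these correlations, so all values below are assumptions.

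| Assumed pattern | r_BE | r_PE | r_PB | One baseline | Two baselines | Extra cut |
|---|---|---|---|---|---|---|
| Equal | 0.5 | 0.5 | 0.5 | 0.750 | 0.667 | 11.1% |
| Equal | 0.6 | 0.6 | 0.6 | 0.640 | 0.550 | 14.1% |
| Equal | 0.7 | 0.7 | 0.7 | 0.510 | 0.424 | 17.0% |
| Equal | 0.8 | 0.8 | 0.8 | 0.360 | 0.289 | 19.8% |
| Moderate decay | 0.5 | 0.35 | 0.4 | 0.750 | 0.723 | 3.6% |
| Moderate decay | 0.7 | 0.55 | 0.6 | 0.510 | 0.484 | 5.2% |
| Moderate decay | 0.7 | 0.5 | 0.6 | 0.510 | 0.500 | 2.0% |
| Moderate decay | 0.9 | 0.75 | 0.8 | 0.190 | 0.187 | 1.3% |
| First-order autoregressive | 0.7 | 0.35 | 0.50 | 0.510 | 0.510 | 0% |

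In the autoregressive row r_PE = r_BE × r_PB, so the Phase I value adds nothing once the Phase II baseline is known. The correlations there use gaps of 11.5 and 6 months: r_PB = 0.7^(11.5/6) ≈ 0.50.

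Under equal correlation the gain is worth 80/(1 − 0.111) ≈ 90 to 80/(1 − 0.198) ≈ 100 children. Under moderate decay with a 5.2% cut it is worth 80/(1 − 0.052) ≈ 84.

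**4. Effect on power at the plan's 0.75 SD.** Power = Φ(3.354/√f − 1.96), where f is the variance fraction.

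- Equal r = 0.5: 0.972 with one baseline (f = 0.750), 0.984 with two (f = 0.667).
- Equal r = 0.7: 0.997 with one (f = 0.510), 0.999 with two (f = 0.424).

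For a smaller true difference of 0.5 SD, which is not the plan's target, simulated power at equal r = 0.6 rises from 78% to 83%.

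**5. What belongs to another choice.** With two time points, the group-by-time test in a repeated measures analysis of variance is equivalent to comparing change scores, with variance fraction 2(1 − r). Moving from that to adjustment for the Phase II baseline takes 1.00 to 0.75 at r = 0.5 and 0.60 to 0.51 at r = 0.7. That step needs no Phase I data and is not counted in the gains above.

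**The case against.** The strongest objection is that nothing in the Protocol is wrong here. Section 2.3.6 leaves its adjustments open, and covariate lists are commonly left to a statistical analysis plan, which may exist and is not shown. A reader might infer that the plan restricts the comparison to the two Phase II waves, or discards the Phase I data. The text does not support that. The Phase II schedule says when measurements are taken. The baseline sentence in 2.3.6 concerns a comparability check and does not define the outcome model. No section places the Phase I values in the comparison, and none excludes them. This part of the objection stands, and it limits the point to a recommendation.

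A second objection is that the gain may be nil. The Phase I value is 9 to 13 months older than the Phase II baseline, in growing children, against a follow-up of 6 months. Equal correlation is therefore the favourable end of the range. This stands too. The zero-gain case is nevertheless a special one: it assumes pure autoregressive decay with no measurement or day-to-day error, and such error is the reason for using a second value.

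A third objection is that the match of variables is not fully shown. Section 2.3.3.1 lists weight, height and BMI, diet, KIDMED, the blood and urine metabolome and the microbiome. It does not name glucose, insulin, A1C or HOMA-IR as Phase I measurements, and 2.3.6 does not tie its regressions on those variables to Phase I. So the Phase I laboratory panel must be confirmed before its values can be named as covariates. Diet is safer, since both candidate dietary methods are collected in Phase I.

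**Conclusion.** The point holds as an optional efficiency gain. By the described flow, each randomised child has a Phase I assessment taken before randomisation, and 2.3.6 states no use of it in the Group A versus Group B comparison.

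The extra reduction in residual variance beyond the Phase II baseline is about 0-5% if correlation decays over the 9 to 13 month gap, and 11-20% if the three waves are equally correlated at 0.5 to 0.8. Every one of these figures rests on assumed correlations. A gain is most plausible for laboratory and dietary end points, where day-to-day noise is large. For weight and BMI, growth over the gap makes the low end more likely.

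A reader might also infer that the trial is underpowered without the Phase I values. It is not, on its own assumptions: 80 children give 0.912 to 0.918 power at 0.75 SD with no baseline adjustment at all.

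**What to change.** In 2.3.6, pre-specify that each Phase II end point is compared between groups in a model that adjusts for the child's Phase II baseline value and, where the same variable was measured in Phase I, for the child's Phase I value as a second pre-randomisation covariate. State which end points have a Phase I counterpart, after confirming the Phase I laboratory panel. Naming the covariates now also avoids choosing them after the results are seen.

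The correlation between the Phase I and Phase II baseline values can be estimated from data pooled across groups, without unblinding, which would show how far the two values agree over the gap.

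The cost is one sentence, one degree of freedom per model (residual degrees of freedom fall from 80 − 3 = 77 to 80 − 4 = 76) and a rule for children whose Phase I value is missing, so that none is dropped from the comparison for that reason. No new data are needed, and the sample size need not change.
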